# 9. STUDY ASSESSMENTS AND PROCEDURES

### 9.1. Screening Assessments

### 9.1.1. Medical History

Medical history will be documented based on subject report and investigator's assessment.

### 9.1.2. Masquerading Disorders Tool

The Masquerading Disorders Tool (Analgesic Solutions, Wayland, MA) is a screening instrument to help identify subjects with disorders that masquerade as painful diabetic peripheral neuropathy, such as Morton's neuroma, peripheral vascular disease, Achilles tendonitis, arthritis, and tarsal tunnel syndrome. The screening instrument consists of symptom screening questions and an inclinic history and examination to target the nature and etiology of the subject's peripheral pain. The results of this assessment tool are provisional, with the final decision based on the clinical judgment of the Investigator.

### 9.1.3. Michigan Neuropathy Screening Instrument

The Michigan Neuropathy Screening Instrument (MNSI) is a 15-item, self-administered questionnaire and a 5-item clinician-administered lower extremity examination that includes inspection of vibratory sensation and ankle reflexes. It can be used to assess distal symmetrical peripheral neuropathy in diabetes [Herman 2012].

### 9.1.3.1. MNSI Modified Scoring

On the self-administered questionnaire, 'Yes' responses to questions 1–6, 8–12, 14–15 are each counted as one point, and 'No' responses to questions 7 and 13 each count as one point. On the lower extremity examination, responses for the left and right feet were combined for the following measures of the examination: ulceration, ankle reflex, vibration perception at great toe, and monofilament. Ulceration was scored as one point if present in either lower extremity. Ankle reflex was scored as 0.5 point if present/reinforcement in one lower extremity and one point if absent in one or both lower extremities. Vibration was scored as 0.5 point if decreased in one lower extremities. Monofilament was scored as 0.5 point if reduced in one lower extremity and one point if absent in one or both lower extremities. Monofilament was scored as 0.5 point if reduced in one lower extremity and one point if absent in one or both lower extremities. (Appearance from the clinical examination is not scored.)

The self-administered questionnaire has a maximum score of 15 points, and the clinical examination has a maximum score of 4 points, resulting in a total maximum possible score on the MNSI of 19 points [Herman 2012].

# 9.2. Efficacy Assessments

### 9.2.1. Numeric Rating Scale of Pain Intensity

The NRS of pain intensity is a unidimensional, segmented numeric version of the visual analog scale. A subject selects a whole number (0 to 10) that best indicates the intensity of his/her pain. The format consists of a horizontal line that is anchored by terms defining pain levels, where

0 represents no pain and 10 represents worst pain imaginable.

Subjects will report at bedtime their average pain intensity, worst pain intensity, and average pain upon walking during the past 24 hours, using the 11-point NRS.

### 9.2.2. Patient Global Impression of Change

The PGI-C is a 7-point scale that allows subjects to rate the change in the disease state from study initiation to specific time points during the study or at the end of the study. It provides the subject's impression of overall change since beginning the study [Guy W 1976].

### 9.2.3. Norfolk Quality of Life Questionnaire – Diabetic Neuropathy (QOL-DN)

The Norfolk QOL-DN is a 47-item, subject-reported questionnaire designed to measure the relationship between symptomatic diabetic neuropathy and quality of life from the perspective of the patient. It is composed of 2 parts: questions related to symptoms experienced by the patient and questions related to the impact of the patient's neuropathy on activities of daily life. A factor analysis performed on the Norfolk QOL-DN separated the questions into 5 domains: activities of daily living, symptoms, small fiber neuropathy, large fiber neuropathy, and autonomic neuropathy. The QOL-DN is sensitive to the different features of diabetic neuropathy including small fiber, large fiber, and autonomic nerve function [Vinik 2005]. Aptinyx Confidential Page 48 of 74

### 9.2.4. Daily Sleep Interference Scale

The DSIS was developed to quantify sleep interference due to pain. The DSIS is a single -item measure that is completed by patients once a day (upon awakening) to accurately capture variability in sleep interference due to pain on a daily basis, thus minimizing recall bias. The DSIS has an 11-point response scale that asks patients to "Select the number that best describes how much your pain has interfered with your sleep during the past 24 hours." Response options range from 0 (did not interfere with sleep) to 10 (completely interfered with sleep/unable to sleep due to pain). The DSIS is designed to be used in a patient daily diary that patients fill out upon awakening each morning [Vernon 2008].

#### 9.2.5. Brief Pain Inventory for Diabetic Peripheral Neuropathy

The BPI-DPN is a patient-completed numeric rating scale that assesses the severity of pain (Severity scale), its impact on daily functioning (Interference scale), and other aspects of pain (e.g., location of pain, relief from medications). A modified version of the BPI-DPN, including the 4item pain Severity scale (Worst Pain, Least Pain, Average Pain, and Pain Now) and the 7-item pain Interference scale (General Activity, Mood, Walking Ability, Normal Work, Relations With Others, Sleep, Enjoyment of Life) has been validated in patients with painful diabetic peripheral neuropathy) and distinguishes between pain due to diabetic peripheral neuropathy and pain due to other causes. Each item uses a 0 to 10 numeric rating scale anchored at 0 for "no pain" and 10 for "pain as bad as you can imagine" for Severity, and "does not interfere" to "completely interferes" for Interference. The 4 Severity items and the 7 Interference items can also each be averaged to form 2 composite scores, the Pain Severity Index and the Pain Interference Index [Zelman 2005].

#### 9.2.6. Patient Global Impression of Severity (PGI-S)

PGI-S is a global index used to rate the severity of a specific condition (a single-state scale), on which (1) corresponds to "normal", two (2) corresponds to "mild", three (3) corresponds to "moderate" and four (4) corresponds to "severe" [Guy W 1976].

### 9.2.7. Pain Catastrophizing Scale (PCS)

The PCS is a 13-item instrument that assesses the state of mind of patients in pain through a comprehensive evaluation instrument that encompasses the different perspectives on catastrophizing. Factor analyses of the PCS have shown that catastrophizing can be viewed as a multidimensional construct comprising elements of rumination ("I can't stop thinking about how much it hurts"), magnification ("I worry that something serious may happen"), and helplessness ("There is nothing I can do to reduce the intensity of the pain"). The PCS instructions ask participants to reflect on past painful experiences, and to indicate the degree to which they experienced each of 13 thoughts or feelings when experiencing pain, on 5-point scales with the end points (0) not at all and (4) all the time. The PCS total score is computed by summing responses to all 13 items. PCS total scores range from 0 - 52. The PCS subscales are computed by summing the responses to rumination, magnification, and helplessness items [Sullivan 1995].

## 9.3. Safety Assessments

### 9.3.1. Safety Parameters

Refer to the Table 3 (Schedule of Procedures) or Section 10 (Schedule of Procedures) for time points.

Aptinyx Confidential

#### 9.3.2. Vital Sign Measurements

Each assessment includes blood pressure and pulse after sitting or lying supine for at least five (5) minutes and prior to blood sample collection. Vital signs may be repeated up to three (3) times at screening, per the Investigator's discretion. There should be a minimum of five (5) minutes of rest allotted in between measurements. All vital signs should be recorded in the subject's source documents, with the final measurement of vital signs being entered into the eCRF system.

#### 9.3.3. Physical Examination

A complete physical examination will include assessment of the following body systems: head, eyes, ears, nose, and throat; lymph nodes; neurologic, respiratory, cardiovascular, gastrointestinal, musculoskeletal, and dermatologic systems; and extremities.

The complete physical examination at Visit 1 will include a comprehensive neurological examination of the following: cranial nerves, muscle strength and tone, sensory function, coordination, gait, reflexes, and mental status.

A brief physical examination will be completed at Week 12/Early Termination.

For measuring weight, a calibrated scale with appropriate range and resolution will be used. Subjects must remove shoes and bulky layers of clothing

Height will be measured without shoes.

#### 9.3.4. Electrocardiogram

Triplicate ECGs with a minimum of a two minute interval between each ECG will be collected at screening, and a standard 10-second ECG will be collected at baseline, week 8 and week 12/ET after at least five (5) minutes of supine rest and prior to blood sample collection, if possible. The device will be a Spaulding (Spaulding Medical, West Bend, WI) electrocardiogram (ECG) device that acquires a 12-lead ECG. The ECG data will be submitted to the designated ECG laboratory cardiologists for measurements and diagnoses.

The Principal Investigator or qualified Sub-investigator will review all ECG interpretations and interval duration measurements for clinical significance. Standard ECG parameters will be measured. Clinically significant, abnormal 12-lead ECGs should be repeated. Clinically significant ECG changes should be recorded as an adverse event.

The Spaulding ECG device should be used for all assessments during the study unless it is nonoperational, in which case another ECG may be performed locally and transmitted to Spaulding for central reading via printout.

#### 9.3.5. Clinical Laboratory Assessments

Blood samples for hematology and chemistry will be obtained after an 8-hour fast.

The study investigator should monitor subjects during the study for signs of hepatic abnormality potentially meeting the stopping criteria (Section 11).

The investigator will review clinical laboratory test results as they become available, for determination and documentation of clinical significance (if there are out of range values). The investigative site will contact the medical monitor for any liver function test results that potentially meet the stopping criteria. Possibly drug-related or clinically significant abnormal values of uncertain causality must be repeated. Persistent abnormal laboratory values should be followed at Aptinyx Confidential Page 50 of 74

the investigator's discretion. Abnormal liver function tests (specified in Section 11) must be repeated within 48-72 hours.

Hematology assessments will include hemoglobin, hematocrit, red blood cell count, white blood cell count, differential (neutrophils, lymphocytes, monocytes, eosinophils, and basophils), and platelet count. Hemoglobin A1c will be assessed at Visit 1 and Visit 6/Early Termination.

Chemistry assessments will include glucose, calcium, electrolytes (sodium, potassium, bicarbonate, chloride), phosphorus, blood urea nitrogen (BUN), creatinine, creatinine clearance, albumin, total protein, magnesium, alkaline phosphatase (ALP), aspartate aminotransferase (AST), alanine aminotransferase (ALT), lactate dehydrogenase, gamma-glutamyl transferase (GGT), albumin, total bilirubin, direct bilirubin, indirect bilirubin, uric acid, and C-reactive protein (CRP). Triglycerides and a thyroid panel (TSH, T3, T4, and free T4) will also be measured at Visit 1.

Qualitative urinalysis will include pH, specific gravity, glucose, ketones, protein, blood, leukocyte esterase, urobilinogen, nitrites, and reflex microscopy.

Abnormal clinical laboratory tests at screening may be repeated, on a case by case basis, after consultation with the Medical Monitor.

Hepatitis B screening will include both the hepatitis B surface antigen (HBsAg) and the hepatitis B core antibody (HBcAb) testing. If HBsAg and HBcAb are both positive, the subject is not eligible Additional testing for Hepatitis B surface antibody (HBsAb) will be done in case of a positive test result for either HBsAg or HBcAb, but not both. Subjects positive for HBcAb and negative for HBsAg, but also negative for hepatitis B surface antibody are not eligible for entry into the study. In addition, if either HBsAg or HBcAb are positive, a confirmatory HBV DNA reflex test will be completed. If the HBV DNA test is positive, the subject will not be eligible.

A history of or a positive test result at Screening for the hepatitis C virus antibody indicating ongoing infection will result in confirmatory testing for hepatitis  $C_m RNA$ . Subjects with negative hepatitis  $C_m RNA$  will be eligible for entry into the study.

If the screening test for HIV antibody is positive, confirmatory test may be performed.

Female subjects of childbearing potential will receive urine pregnancy tests ( $\beta$ -human chorionic gonadotropin) at Visit 1, Visit 2, and Visit 6. Testing may be performed at other visits, if clinically indicated.

The urine drug screen will include benzodiazepines, psychoactive cannabinoids (e.g., marijuana,THC), PCP, opioids, cocaine and amphetamines.

### 9.3.6. Sheehan-Suicidality Tracking Scale

The standard version of the S-STS [Sheehan 2014] is a 16-item scale that assesses the seriousness of suicidality phenomena on a Likert-type scale (0 to 4) ranging from 0 = not at all to 4 = extremely. It also assesses the frequency of key phenomena and the overall time spent in suicidality. The standard version is available in identical clinician- and subject-rated formats.

The S-STS accommodates a wide range of time frames. In clinical studies, the frequently used variants are "in the past week," "in the past month," "since the last visit," "lifetime look back," and "in the past day".

Suicidality identified after baseline will be recorded as an adverse event.

#### 9.3.7. Abuse and Diversion Assessment

Potentially aberrant drug behavior (i.e., misuse and abuse-related events) will be identified, assessed, and quantified using MADDERS, which consists of a set of forms completed by Investigators or qualified Subinvestigators when potential abuse-related events are identified and upon the completion of each subject's participation in the study. Potential abuse-related events will be adjudicated by an independent committee [Smith 2017; Treister 2016].

Any misuse and abuse-related event will be recorded as an adverse event.

### 9.4. Safety and Pharmacovigilance

#### 9.4.1. Adverse Events – Relationship to Study Drug

An adverse event is any untoward, undesired, unplanned clinical event in the form of signs, symptoms, disease, or laboratory or physiological observations occurring in a human being participating in a clinical study with an Aptinyx study drug, regardless of causal relationship.

Laboratory abnormalities are not considered adverse events unless they are associated with clinical signs or symptoms or require medical intervention. However, a laboratory abnormality (e.g., a clinically significant change detected on clinical chemistry, hematology, or urinalysis results) that is independent from the underlying medical condition and that requires medical or surgical intervention, or leads to study drug interruption or discontinuation, must be considered an adverse event.

The causality of each AE should be assessed and classified by the Investigator as "related" or "not related." An adverse event is considered related if there is a reasonable possibility that the event may have been caused by the study drug under investigation (i.e., there are facts, evidence, or arguments to suggest possible causation). There is also a timely relationship to the administration of the investigational drug and the event follows a known pattern of response for which no alternative cause is present.

#### Not Related

• There is no reasonable possibility that the study drug under investigation may have caused the event. The event is obviously explained by another cause or the time of occurrence of the AE is not reasonably related to administration of the study medication.

#### Related

• There is a reasonable possibility that the study drug under investigation caused the event (i.e., there are facts, evidence, or arguments to suggest possible causation). There is also a timely relationship to the administration of the investigational drug and the event follows a known pattern of response for which no alternative cause is present.

When an assessment is not provided, the event will be treated as related for purposes of regulatory reporting.

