Overall, NYX-2925 appears to be safe and well tolerated at oral doses up to 200 mg daily for up to 4 weeks. Across the studies, there have been few severe treatment-emergent adverse events (TEAEs), serious adverse events (SAEs), or TEAEs leading to study discontinuation, and no deaths. The most commonly reported TEAEs have been headache, diarrhea, upper respiratory tract infection, alanine aminotransferase increased, arthralgia, abdominal distension, anxiety, and eructation. No subject reported a SAE while receiving NYX-2925. An NYX-2925-2001 related TEAE leading to study discontinuation (severe headache) was reported, which occurred for a subject receiving daily NYX-2925 10 mg in study NYX-2925-2001. One NYX-2925-2002 subject had an unrelated TEAE of mild ventricular extrasystoles leading to study discontinuation with onset during the placebo period and was discontinued after 1 dose of NYX2925 20 mg.

No clinically meaningful changes in vital sign measurements, safety 12-lead electrocardiogram (ECG) results, physical examination findings or suicidality have been observed after a single dose of NYX-2925. Few potentially clinically significant laboratory results were observed during 4 weeks of treatment in study NYX-2925-2001; however, these were generally comparable across treatment groups. A single subject in the NYX-2925 10 mg group had elevated clinical laboratory results, including alanine aminotransferase increased and aspartate aminotransferase increased, that met investigative product stopping criteria. On the NYX-2925-2002 study, one (4.8%) subject had a potentially clinically significant GGT result in the NYX-2925 200 mg period and also experienced elevated ALT and AST. These elevations occurred during the NXY-2925 200 mg period and declined following the end of dosing; however, GGT remained above the laboratory reference range at last evaluation, though trending downward.

In summary, NYX-2925 has been sufficiently tested in preclinical studies for safety and tolerability over a wide dose range, with exposures greater than the proposed clinical doses. General toxicology studies in rats and dogs support clinical studies up to and including 13 weeks of daily doses. Clinical results to date indicate that NYX-2925 is safe and well-tolerated. The preclinical, Phase 1 and Phase 2 clinical data support further testing in patients with painful peripheral diabetic neuropathy.

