The serious adverse event report should provide as much of the required information as is available at the time. The following minimum information is required for reporting a serious adverse event: subject identification, reporting source, and an event outcome. Supplemental information may be transmitted using a follow-up report and should not delay the initial report. Aptinyx may contact the investigational site to solicit additional information or to follow-up on the event.

If there is any doubt whether the information constitutes a serious adverse event, the information will be treated as a serious adverse event for the purposes of this protocol. Serious adverse event reporting will begin at the time of consent and will end 30 days after the last dose.

All relevant documentation pertaining to a serious adverse event (e.g., additional diagnostic tests, consultation reports, discharge summaries, and postmortem reports) will be provided to the Sponsor-designated Medical Monitor in a timely manner. Serious adverse events will be followed until resolution or return to baseline (when worsening of a pre-existing condition is reported). If a serious adverse event does not return to baseline but reaches a stable situation that is not expected to change, this may be documented on the serious adverse event form.

The Sponsor may break the treatment code for subjects who experience a serious adverse event in order to determine if the individual case or group of cases requires expedited regulatory reporting. Individual treatment codes will be available to limited staff who are responsible to break codes for reporting purposes.

For each SAE, the Investigator and Sponsor will independently assess whether there is a reasonable possibility that the event may have been caused by the study drug ("drug-related"). The Sponsor will evaluate each drug-related SAE to determine if the event was unexpected. If the SAE is assessed to be both drug-related and unexpected, the Sponsor or designee will notify all

Investigators, and will report it to the appropriate regulatory authorities as required by applicable local regulations. The Sponsor or designee will report SAEs, including narratives, to the U.S. FDA and local regulatory authorities as required by 21 CFR 312.32 and the International Conference on Harmonisation (ICH) Guideline for Good Clinical Practice. The Investigator is responsible for notifying his/her respective IRB.

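### Protocol Section 9.4.1 gives two conflicting tests for a related adverse event, departs from Section 9.5, and leaves some events outside both causality categories

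*Protocol*

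**What the plan says.** Protocol Section 9.4.1 provides two categories, Related and Not Related, and nothing between them. Its opening test is worded as sufficient: "An adverse event is considered related if there is a reasonable possibility that the event may have been caused by the study drug under investigation".

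The same paragraph, and again the definition under the Related subheading, goes on to say that there is also a timely relationship to dosing and that "the event follows a known pattern of response for which no alternative cause is present".

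The Not Related definition has two sentences. The first is "There is no reasonable possibility that the study drug under investigation may have caused the event". The second begins "The event is obviously explained by another cause or the time of occurrence of the AE is not reasonably related to administration".

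Where no assessment is given, Section 9.4.1 treats the event as related for regulatory reporting. SAP Section 6.12.1 does the same for analysis.

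Protocol Section 9.5 deals with serious events separately. Investigator and sponsor each judge independently whether there is a reasonable possibility of causation, with no condition on pattern or alternative cause. The notification and regulatory reporting step begins "If the SAE is assessed to be both drug-related and unexpected".

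SAP Section 6.12.1 defines a treatment-related adverse event as one that the investigator classified as related.

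**The concern.** Two categories should cover every event and should not depend on which sentence the investigator reads last. Here the Related definition can be read as a list of conditions that must all hold, while Not Related is closed to any event with a reasonable possibility of causation. A new kind of event has no recognised pattern to match. In this population, possible other causes are also common: all subjects have type 2 diabetes, they may continue antidiabetic drugs (Protocol Section 8.7), and they are dispensed acetaminophen.

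Safety and tolerability of 50 mg once daily is listed under the primary objective. The treatment-related TEAE tables depend directly on this classification. If sites apply different tests to similar events, those tables mix two definitions. If investigators settle the doubtful events as Not Related, the tables run low.

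**Working it through.** No arithmetic applies. The check sets the definitions side by side and runs event types through them.

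**Inputs**
- Opening test, Protocol 9.4.1: reasonable possibility is sufficient.
- Related definition, read jointly: reasonable possibility, plausible timing, a known pattern, and no alternative cause.
- Not Related, first sentence: no reasonable possibility. Second sentence: an obvious other cause, or implausible timing.
- Protocol 9.5, serious events only: reasonable possibility alone.

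**Event types, all with plausible timing**

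| Event | 9.4.1 opening test | 9.4.1 Related, read jointly | 9.4.1 Not Related | 9.5, if serious |
|---|---|---|---|---|
| A. Reasonable possibility, known pattern, no other cause | Related | Met | Not met | Drug-related |
| B. Reasonable possibility, no known pattern, no other cause | Related | Not met | Not met | Drug-related |
| C. Reasonable possibility, known pattern, possible but not obvious other cause | Related | Not met | Not met | Drug-related |
| D. Reasonable possibility, no known pattern, possible but not obvious other cause | Related | Not met | Not met | Drug-related |
| E. Obvious other cause, so no reasonable possibility | Not related | Not met | Met | Not drug-related |
| F. No reasonable possibility, no obvious other cause | Not related | Not met | Met only if the first sentence is enough by itself | Not drug-related |

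Types B, C and D show the gap. They are related under the opening test and, if serious, drug-related under Section 9.5. On the joint reading they meet neither category in 9.4.1. Type F shows a smaller fault on the other side: if the second sentence of Not Related is also a condition, an event with no reasonable possibility has no home either.

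**Direction.** The joint test is the opening test plus further conditions. Events that pass it are therefore a subset of those that pass the reasonable-possibility test. Applying it can only lower the count of related events, never raise it.

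**The defaults.** A blank assessment is counted as related. That protects an event of type B, C or D only if the investigator leaves the field empty. It does nothing once Not Related has been ticked.

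**What the classification feeds.** SAP Section 6.12.1 uses it for treatment-related TEAEs overall, by system organ class and preferred term, and by maximum severity, and for serious treatment-related TEAEs. Protocol Section 12.7.1 lists a drug-related table as well. Tables of all TEAEs, serious TEAEs, TEAEs leading to study drug discontinuation, early withdrawals and deaths do not use it. Nor do the safety endpoints in Protocol Section 5.3.3 and SAP Section 3.4.

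**The case against.** The strongest reply is that the opening sentence already settles the matter: reasonable possibility is enough, and what follows is loosely joined description. That reading is available, so it would be wrong to say that the protocol allows Related only where a known pattern exists. But the extra conditions appear twice, once inside the definition that investigators are meant to apply. On this reading the section contradicts itself, and the remedy is the same.

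A second reply is that the second sentence of Not Related sends events with an obvious competing cause to that category. This stands, and it narrows the gap to events with no recognised pattern or with another cause that is possible but not obvious.

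Three stronger inferences are tempting, and the documents do not support them.

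- *That an event can hardly ever be both related and unexpected, so expedited reporting fails.* Section 9.5 sets its own test, without the pattern or other-cause conditions, adds an independent sponsor judgment, and provides for drug-related unexpected serious events. In addition, the protocol does not define a known pattern. It could cover the dissociative symptoms described in Section 9.4.2 or the liver findings from 13 weeks of dosing in dogs (Section 4), and matching a pattern is not the same as being expected. What remains is the risk that an investigator carries the 9.4.1 wording into the judgment of a serious event.
- *That Weeks 5 to 12 have no pattern to match.* Section 4 describes the drug as "safe and well tolerated at oral doses up to 200 mg daily for up to 4 weeks", and this trial doses for 12 weeks, so 12 − 4 = 8 weeks lie beyond that experience. But a pattern does not expire at Week 4. Headache, diarrhea or raised ALT at Week 9 would match events already reported.
- *That the tolerability conclusion is biased toward safety.* The trial is double-blind and placebo-controlled, and the all-causality tables by arm make the main safety comparison without using relatedness.

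**Conclusion.** The point holds as an inconsistency within Section 9.4.1, and between 9.4.1 and 9.5, that leaves some events outside both categories. Its reach is limited to the treatment-related TEAE tables and to possible spill-over into investigators' judgments of serious events.

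The direction is known on the joint reading: related counts can only fall relative to a reasonable-possibility standard. The size is not known. It depends on how many events are of types B to D and on how sites resolve them, and the documents give neither. Counting rows in the table above is not a measure of size, because the rows carry no frequencies.

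The verdict assumes that at least some investigators read the Related definition as a joint list, which is its natural reading, and that they tick a category rather than leave the field blank. It is worth correcting because it is a stated rule that can misclassify events, and the correction is cheap.

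**What to change.** Bring Section 9.4.1 into line with the standard that Section 9.5 already uses.

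1. In the opening paragraph and in the Related definition, remove the known-pattern and no-alternative-cause conditions.
2. Recast timing, in both places, as a factor that informs the judgment of reasonable possibility.
3. Recast the second sentence of Not Related in the same way, so that an obvious other cause or implausible timing becomes a reason for finding no reasonable possibility. Without this step the two categories would still not be exact complements (type F above).
4. Where site instructions repeat the definition, use the same wording. If events have already been classified when the change is made, say whether they will be reassessed before unblinding.

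The cost is a wording amendment. The downside is that somewhat more events will be classed as related, in both arms. No change to the SAP's definition of treatment-related is needed, since it takes the investigator's classification as given.
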